**NCT03870048 tDCS to Lower Neuropathic Pain and Fatigue in People With Multiple Sclerosis**

Prospective participants, men and women with MS, will be recruited. To accomplish this study, 20 participants will need to complete 3 randomly-ordered blocks of protocols (sham, 2 mA, 4 mA), separated by at least one week. Each block involves 5 daily sessions at the INPL. The duration of each session will be approximately one hour and will be completed at the same time of day for each subject. We expect data collection to last 6 months. Each session will be a combination of questionnaires, leg strength assessment, and an isokinetic fatigue test.

Leg strength assessment: Isokinetic (concentric/concentric) flexion and extension of the knee at 60°/s will be performed five times to determine the more-MS affected leg. When strength difference between the left and right legs is less than 10%, the more affected side will be based on the participant's self-report.

Isokinetic fatigue test: Participant's will perform 40 consecutive repetitions of isokinetic concentric/concentric flexion and extension of the knee on the more-affected leg at 120 degree/sec.

In the initial session (i.e., Block 1, Session 1) subjects will 1) be consented, 2) complete the Patient Determined Disease Steps (PDDS) questionnaire, 3) the Fatigue Severity Scale (FSS), 4) Neuropathic Pain Questionnaire (NPQ), 5) Visual analog scale (VAS), 6) perform a leg strength assessment, 7) perform an isokinetic fatigue test, and 8) undergo either sham tDCS, tDCS at 2 mA, or tDCS at 4 mA, depending on the randomized block.

tDCS treatment protocol: A tDCS device (Soterix) will deliver a small direct current through two sponge surface electrodes (5cm × 5cm, soaked with 15 mM NaCl). The positive electrode will be placed over the motor cortex representation of the more affected leg, and a second electrode will be placed on the forehead above the contralateral orbit. The three protocols blocks (sham, 2 mA, 4 mA) will be performed in randomized order.

tDCS Block: The participant will receive tDCS for 20 min at an intensity of 2 mA or 4 mA while seated comfortably and quietly in a room. The intensity will start at 0 mA and will be incrementally increased to 2mA or 4 mA over the initial 30 seconds. At the 19:30 minute time point, the current will gradually be reduced from 2 mA (or 4 mA) to 0 mA.

Sham block: Identical to the tDCS block, except the participants will only receive the initial 30 seconds of ramp-up, after which the current will be set to 0 for the remainder of the 20 minutes.

The remaining sessions of first block (i.e. Block 1, Sessions 2-5) will be as follows: In Sessions 2 and 4, the subjects get the tDCS or sham treatment, after which they will complete the fatigue and pain questionnaires (FSS and NPQ). Sessions 3 will be the same as Sessions 2 and 4, except that the isokinetic fatigue test will be performed at the beginning (i.e., before the tDCS or sham treatment). Session 5 will start with tDCS or sham treatment, then the isokinetic fatigue

test, and finally the fatigue and pain questionnaires.

Blocks 2 and 3 will be completed in the same manner as Block 1, except that the subjects will not redo the PDDS, VAS, and BDI in Session 1 and the treatment will shift to either tDCS at 2 mA, tDCS at 4 mA, or sham, depending on how the blocks were randomized. Block 2 will be randomly assigned based on uncompleted stimulation blocks.

Duration of Relief – If the participant indicates any reduction in pain following the previous day's tDCS session, they will be asked to estimate how long their pain was reduced following the session. Additionally, one week following the last testing session (i.e., Block 2, Session 5), participants will be contacted via telephone and asked the following questions:

1. Was tDCS effective at reducing your pain?
2. If so, how long did you notice a reduction in pain following your final tDCS session?
3. Have you reduced your use of pain relieving medications since your last tDCS session?

**STATISTICAL ANALYSIS** The generalized estimating equation (GEE) framework will be utilized to assess changes over time in fatigue and quality of life measures. An interaction term between time and treatment will allow us to test the within and between-treatment differences over all time points. Using histograms, variable distributions will be assessed to decide which link function to specify when modeling each outcome. To account for the inherent correlation that occurs in repeated measures data, we will cluster on subject ID. In addition to examining the unadjusted relationship between the time-treatment interaction and each outcome, we will consider the addition of control variables, which will reduce the likelihood of unaccounted confounders. The control variables being considered for inclusion in the adjusted models are age, sex, and time since discharge/discontinuation of home isolation. For each outcome, models will be fit for all possible combinations of control variables. The predictor set that yields the smallest Akaike information criterion (AIC) will be considered the optimal control variable set to adjust associations between the main predictor and the outcomes. Statistical significance will be assessed at the  $\alpha = 0.05$  level. Analyses will be conducted using SAS 9.4.

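### The stated draw from the remaining conditions does not balance the six orders over 20 people, and the model has no block term: a small, cheaply avoided loss of precision

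*Combined protocol and SAP*

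**What the plan says.** The opening paragraph of the combined protocol and SAP calls for 20 people who complete all three blocks, and the tDCS treatment protocol paragraph adds that "The three protocols blocks (sham, 2 mA, 4 mA) will be performed in randomized order". The paragraph on Blocks 2 and 3 says that "the treatment will shift to either tDCS at 2 mA, tDCS at 4 mA, or sham, depending on how the blocks were randomized", and then: "Block 2 will be randomly assigned based on uncompleted stimulation blocks". Blocks are "separated by at least one week".

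There is no mention of counterbalancing, a Latin square, permuted blocks of orders or a list prepared in advance.

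Under Statistical Analysis, the outcomes go into a GEE clustered on subject. "An interaction term between time and treatment will allow us to test the within and between-treatment differences over all time points". On covariates: "The control variables being considered for inclusion in the adjusted models are age, sex, and time since discharge/discontinuation of home isolation". Block number, sequence and carryover do not appear.

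**The concern.** A draw from whatever a person has not yet received balances conditions within that person only. Across 20 people nothing stops sham from falling mostly early or mostly late.

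That matters if results move from block to block for reasons other than stimulation. Each block has the 40-repetition fatigue test in Sessions 1, 3 and 5 and the FSS and NPQ in all five sessions. Each person therefore does the test 3 × 3 = 9 times and each questionnaire 5 × 3 = 15 times. Practice, fading novelty and regression to the mean are all plausible. With no block term in the model, such a trend combined with unequal positions adds noise to any comparison of levels between conditions.

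**Working it through.** **Inputs.** From the opening paragraph: 20 completers and three conditions, so 3! = 6 orders. Assumption: each order has probability 1/6, independently between people (the documents give no probabilities). The drift per block, d, is not in the documents, so results are given as multiples of d. The plan states no figure for order balance, and no effect size, SD or power behind the 20, so there is no figure of its own to reproduce.

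**1. Gap in block position.** For one person, the block number of sham minus that of 4 mA is ±1 in four orders and ±2 in two.
- Variance per person: (4 × 1 + 2 × 4)/6 = 2.
- SD of the mean over 20 people: √(2/20) = 0.316 blocks.

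**2. How often the gap is noticeable.**
- A gap of at least 0.5 block means that the 20 differences sum to at least 10 in absolute value. This happens in about 13% of trials.
- Some pair of the three conditions is at least 0.5 block apart in 29% (simulation).
- At least one order is unused: 6(5/6)^20 − 15(4/6)^20 + 20(3/6)^20 = 15.2%.
- Sham in Block 1 is Binomial(20, 1/3): mean 6.67, SD √(20 × 1/3 × 2/3) = 2.11, central 95% range 3 to 11 people.

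**3. Effect with no block term.**
- Sham versus 4 mA, comparing levels: added error SD 0.316 × d, about 0.32d.
- Sham versus the average of the two active conditions: variance per person 1.5, so √(1.5/20) = 0.27d.
- Within-block change: each block has its own measurements before stimulation in Session 1. A shift common to all sessions of a block cancels from the change, so the added error is zero under purely additive drift.

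**4. Effect with block terms.** This uses within-person least squares with block and treatment terms, and variance relative to exact balance (2σ²/20 = 0.1σ², with σ the within-person SD).
- Unrestricted draw: ratio about 1.05 to 1.06 on average and 1.18 at the 95th percentile. In standard error this is √1.06 = 1.03 and √1.18 = 1.09.
- Each order three times plus one mirrored pair: at most 1.008, whichever pair and contrast are chosen.

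**5. Is the test misled?** Take per-person sham versus 4 mA differences with no block term. Their variance is 2σ² + 2d². The drifts of 0.5σ and 1.0σ per block are illustrative.
- Random orders: the true SE is √(2.5/20) = 0.354σ at d = 0.5σ and √(4/20) = 0.447σ at d = σ. The reported SE follows it, and simulated type I error stays near 5%.
- Balanced list, still no block term: the true SE falls to √(2/20) = 0.316σ. The differences between people still carry the order effect, so the reported SE stays at about 0.35σ and 0.46σ. Simulated type I error falls to about 3% and 0.5%.

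A list alone therefore lowers the true error, but the planned analysis would not report the gain.

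**The case against.** Five points can be made for the plan.

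- **Random ordering is unbiased.** A reader might infer that a trend across blocks biases active against sham. It does not: over repeated randomisations the effect averages to zero, and a subject-clustered standard error already counts it (step 5). This stands.
- **The planned contrast may be largely protected.** If *time* in the interaction means session within block, an additive block shift cancels. Order then matters only if the within-block change itself drifts from block to block. *Time* is not defined, so this stands in part.
- **The lack of balance is inferred from silence.** The wording about how the blocks were randomised is compatible with a prepared list. The key sentence names only Block 2, and the follow-up call is tied to the end of Block 2, so the text may have been written for two blocks. This stands as a caveat. Still, the one specific rule given is a draw from the remainder, and that rule balances nothing across people.
- **A blinding failure is not shown.** A reader might infer that whoever runs the fatigue test learns the condition. The documents do not say who draws, when, or whether that person assesses. Deducing Block 3 by elimination is possible in any three-condition crossover, including one run from a list.
- **Balance cannot be perfect.** Twenty is not a multiple of six, so some cells must differ, and dropout disturbs any list. This stands, and the fix has to allow for it.

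**Conclusion.** The point holds as a cheap improvement in precision. It is not a flaw in validity. Under the stated rule, read as equal-probability independent draws, a position gap of half a block between sham and 4 mA arises in about one trial in eight.

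The size of the harm depends on two things that the documents leave open: the drift per block, and whether inference rests on levels or on within-block change. For levels with no block term, the added error has SD about 0.32d; for within-block change it may be nil. With block terms, the average loss is about 3% in standard error. Larger losses could be computed for a model with carryover terms, but the plan contains none, so they are not claimed here.

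**What to change.** Replace the sentence on Block 2 with text such as:

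> Before enrolment, a computer-generated list assigns each participant number one of the six orders of sham, 2 mA and 4 mA. Each order occurs three times among the first 18 numbers, and the last two numbers receive a mirrored pair of orders. The list is released one block at a time. A replacement takes the order of the participant replaced.

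A mirrored pair is an order and its reverse. With it, all three conditions have the same mean block position, and each condition falls 6 to 8 times in each block. The replacement rule is needed because the 20 are completers.

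In Statistical Analysis, add block (1, 2, 3) as a categorical fixed term in every GEE. It should not be one of the control variables chosen by AIC. Without this term the reported standard error would not reflect the balance.

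Cost: one list prepared once, and two extra model degrees of freedom. Participants, visits and conditions do not change.

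### The statistical section names fatigue and quality of life as its outcomes and leaves out neuropathic pain, one of the trial's two title aims

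*Combined protocol and SAP*

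**What the plan says.** The title gives the trial two aims: "tDCS to Lower Neuropathic Pain and Fatigue in People With Multiple Sclerosis".

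The protocol text schedules pain measurement throughout. The task list for the initial session includes "4) Neuropathic Pain Questionnaire (NPQ), 5) Visual analog scale (VAS", both ahead of stimulation. In Sessions 2 and 4, once treatment is over, "they will complete the fatigue and pain questionnaires (FSS and NPQ". Session 3 follows the same pattern with a fatigue test added at the start, and Session 5 ends with the two questionnaires. Blocks 2 and 3 repeat Block 1, except that "the subjects will not redo the PDDS, VAS, and BDI in Session 1" and the treatment changes.

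In the STATISTICAL ANALYSIS section, one sentence names outcomes. It says that the GEE framework "will be utilized to assess changes over time in fatigue and quality of life measures". The test follows: "An interaction term between time and treatment will allow us to test the within and between-treatment differences over all time points". Later sentences refer to outcomes only generically, for example "For each outcome, models will be fit for all possible combinations of control variables". The candidate control variables are "age, sex, and time since discharge/discontinuation of home isolation".

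**The concern.** The outcomes in the statistical section do not match the trial that the protocol describes. Fatigue appears in both. Pain is in the title and is measured at every session, but the analysis text does not name it. Quality of life is in the analysis text but in no other part of the document.

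At stake is whether the plan commits anyone to testing one of its two stated aims. The data and a suitable model are both there, but nothing in the text joins them. A reader of the eventual results could not tell from this plan whether an NPQ analysis had been intended or added.

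The home-isolation covariate is a smaller mismatch of the same kind: the section refers to something that the protocol does not describe.

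**Working it through.** The plan states no figure on this point, so there is nothing to reproduce. The check sets the two parts of the document side by side and counts scheduled measurements.

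**1. Constructs and instruments**

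| Construct | In title | Instrument in protocol text | Named in STATISTICAL ANALYSIS |
|---|---|---|---|
| Neuropathic pain | yes | NPQ | no |
| Fatigue | yes | FSS, isokinetic fatigue test | yes, as a construct |
| Quality of life | no | none described | yes, as a construct |

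The other instruments in the protocol text are the PDDS, a VAS whose construct is not stated, the BDI and the leg strength assessment. None is described as a quality-of-life measure. The statistical section does not mention pain, the NPQ or the VAS.

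**2. How much NPQ data the plan collects**

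- Per block: 1 at Session 1, before stimulation, plus 4 at Sessions 2 to 5, after stimulation = 5.
- Per person: 5 × 3 blocks = 15, of which 3 × 1 = 3 are before stimulation and 3 × 4 = 12 after.
- In 20 completers: 15 × 20 = 300.
- Tests that name pain: 0.

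**3. Whether another pain measure could stand in**

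The VAS is done once per person, at Block 1 Session 1, ahead of stimulation. With no record in Blocks 2 and 3 it cannot compare sham, 2 mA and 4 mA. The Duration of Relief question is put only to participants who report a reduction. The telephone questions come once, after the last session, and do not separate the three treatments. The NPQ is the only pain scale repeated across all three.

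**4. Whether the stated model fits the NPQ**

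It does. Each person has NPQ records at 5 sessions under each of 3 treatments, and the model has treatment, time and their interaction, clustered on subject. If session is treated as categorical, which is an assumption because the plan does not say, the interaction has (3 − 1) × (5 − 1) = 8 degrees of freedom. What is missing is the statement that the model is applied to the NPQ.

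**5. The covariate**

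The protocol text mentions no discharge, home isolation or date from which such a time could be counted. Three candidates give 2³ = 8 covariate sets per outcome in the AIC search. If this one were deleted, two candidates would give 2² = 4.

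**The case against.** The best reply is that the section is loosely worded but not wrong. It names no instrument at all, not even the FSS. After its opening sentence it speaks generically of each outcome. The protocol collects the FSS and NPQ as a pair, and the title pairs their constructs, so quality of life may be a loose label for the questionnaire that is not about fatigue. This is possible, but the text does not say it. The generic wording refers back to the outcomes already named, and the protocol itself calls the NPQ a pain questionnaire. Fatigue was carried into the analysis text by name and pain was not.

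Several other points on that side stand:

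- The framework, the interaction term, the clustering and the 0.05 level are already fixed. The link function and covariates are left to the data, but equally so for fatigue. The gap specific to pain is whether the NPQ is analysed. A reader might infer that the whole pain analysis is open, or would be chosen with the data in view. The documents do not support that.
- The BDI appears only as an item not redone, so the instrument list may be incomplete. A reader might infer that no quality-of-life instrument is collected. The documents show only that none is described. An undescribed one would not supply the missing pain test.
- An interaction test alone has no direction, and the plan names no contrast of 2 mA or 4 mA with sham. Naming the NPQ does not settle that. It gives pain the same commitment that fatigue already has.
- On the covariate, the documents support asking for a definition or a deletion, and no more.

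**Conclusion.** The point holds as a mismatch in outcome specification. It is more than missing detail, because the section states an outcome set that differs from the trial's. Read literally, it commits to testing a construct with no described instrument and leaves one of the two title aims without a named test, while 300 NPQ records in 20 completers have no analysis assigned to them. That count assumes every completer attends all 15 sessions and completes the NPQ at each.

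No bias, loss of power or change in error rate is claimed, and no stated number in the plan changes. Fatigue is covered, and the model form suits the design.

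A reader might also infer from the home-isolation covariate that the section was carried over from another study. The mismatch is consistent with that, but the documents do not say so and the conclusion does not depend on it. The covariate is a minor point and adds nothing to the weight of the main one.

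**What to change.** In the STATISTICAL ANALYSIS section:

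1. Replace the outcome phrase with *pain (NPQ) and fatigue (FSS, isokinetic fatigue test)*.
2. State that the GEE time-by-treatment model is applied to the NPQ.
3. Keep quality of life only if an instrument is collected, and then name it and say when it is given.
4. Minor: define the time since discharge or end of home isolation by an event and date in this trial, or delete it from the candidate covariates.

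The cost is rewording of that one section. No visit, procedure or measurement is added, because the NPQ is already scheduled at every session. The change should be made before the NPQ data are examined by treatment.

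### The crossover GEE has no block term and leaves time undefined; the cost is precision in treatment comparisons at a session, not systematic bias

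*Combined protocol and SAP*

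**What the plan says.** The opening paragraph of the protocol requires participants to "complete 3 randomly-ordered blocks of protocols (sham, 2 mA, 4 mA), separated by at least one week". The tDCS treatment protocol paragraph repeats that "The three protocols blocks (sham, 2 mA, 4 mA) will be performed in randomized order". Each block has five daily sessions.

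The STATISTICAL ANALYSIS section specifies a GEE clustered on subject ID. On the model terms it says: "An interaction term between time and treatment will allow us to test the within and between-treatment differences over all time points". On covariates: "The control variables being considered for inclusion in the adjusted models are age, sex, and time since discharge/discontinuation of home isolation". On selection among them: "For each outcome, models will be fit for all possible combinations of control variables", with the smallest AIC deciding. The link is also left open: "Using histograms, variable distributions will be assessed to decide which link function to specify when modeling each outcome".

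No block, period or sequence term appears. Nothing says whether time runs 1 to 5 within a block or 1 to 15 over the study, or whether it is categorical or linear.

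Blocks 2 and 3 are run "in the same manner as Block 1, except that the subjects will not redo the PDDS, VAS, and BDI in Session 1". The FSS, NPQ and isokinetic fatigue test are therefore taken before stimulation in Session 1 of every block.

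**The concern.** In a crossover, anything that moves with time on study, such as practice on the fatigue test or familiarity with a questionnaire, can shift outcomes from one block to the next. Participants receive the treatments in different orders, so an unmodelled shift enters the treatment differences as noise. A block factor removes it for two parameters, using information the trial already records.

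There is little precision to spare. The plan gives 20 participants with no power calculation. For scale, a two-sided 5% paired t-test on 20 pairs has 80% power only for a standardised paired difference of 0.66.

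The undefined time variable adds to the problem, because it decides whether block is absent from the model or partly absorbed by it.

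**Working it through.** **Inputs.** From the protocol: 20 participants, three blocks, five sessions per block, random order. From the STATISTICAL ANALYSIS section: the model terms and three candidate covariates. The documents give no effect size, variance, correlation or power, so the figure of 20 cannot be reproduced. Assumed: total SD 1, within-person variance 0.4 (between-block correlation 0.6), identity link, complete data, independent random orders, and a linear shift of d SD per block.

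**1. Can the search add block?** Three candidates give 2 × 2 × 2 = 8 models per outcome. None contains block.

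**2. Treatment comparison at one session, no block term.** Two blocks drawn at random from shifts {0, d, 2d} differ with per-person variance (4d² + 2(2d)²)/6 = 2d². The contrast variance is therefore (2 × 0.4 + 2d²)/20.

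| Shift per block | Variance | SD without block | Simulated SD without block | Simulated SD with block |
|---|---|---|---|---|
| 0 | 0.0400 | 0.200 | 0.201 | 0.205 |
| 0.25 | 0.04625 | 0.215 | 0.217 | 0.205 |
| 0.5 | 0.0650 | 0.255 | 0.257 | 0.205 |

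These simulations used 2,000 trials. A separate set with the same total variances gave 0.193, 0.212 and 0.253 without block and 0.195, 0.199 and 0.201 with it. In that set, at a 0.5 SD shift and an assumed 0.5 SD effect, power was 49% without block and 68% with it.

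In general, omission multiplies the variance by 1 + d²/(1 − rho), where rho is the between-block correlation. For rho from 0.5 to 0.9 the SE multiplier is 1.01 to 1.05 at d = 0.1, 1.06 to 1.28 at 0.25, and 1.22 to 1.87 at 0.5.

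**3. Bias and test size.** Mean error without block was 0.00 (Monte Carlo error 0.004-0.005) at shifts of 0, 0.25 and 0.5 SD. Null rejection at a 0.5 SD shift was 6.1% without block and 5.7% with it.

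**4. Change from Session 1 to Session 5.** A constant shift is present at both sessions and subtracts out. The simulated SD at a 0.5 SD shift was 0.224 with or without block. When the assumed block effect varied by session, the SD was 0.273 either way, so a block main effect does not recover that loss.

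**5. Dropout.** With assumed dropout of 30% after a 4 mA block and 5% after the others, and a 0.5 SD shift, the level contrast was biased by about 0.06 SD without block and 0.01 with it. The change contrast was not biased.

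**6. If time is a 15-level factor.** There are 15 × 3 = 45 cells with 20/3 = 6.7 people each. A comparison at one study session is then between different people. Its SD is √(2/6.67) = 0.55 under an independence working correlation and about 0.42-0.45 under an exchangeable one, against 0.20 within person.

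**7. Session 1 adjustment.** Let r be the within-block correlation. The change score has SD √(4 × 0.4(1 − r)/20). A linear slope over five sessions, scaled to the Session 1-5 change, has SD 4 × √(2 × 0.4(1 − r)/(10 × 20)). The adjusted contrast uses the block's Session 1 value and the participant's mean Session 1 value (simulated, 2,500 trials).

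| r | Change, formula | Change, simulated | Slope, formula | Adjusted, simulated |
|---|---|---|---|---|
| 0.3 | 0.237 | 0.234 | 0.212 | 0.196 |
| 0.5 | 0.200 | 0.204 | 0.179 | 0.180 |
| 0.7 | 0.155 | 0.149 | 0.139 | 0.142 |

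The simulated SD ratio of change to adjusted is 0.234/0.196 = 1.19, 0.204/0.180 = 1.13 and 0.149/0.142 = 1.05. Against the slope, the gain is gone at r = 0.5 and 0.7 if the effect builds linearly.

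**The case against.** The strongest reply is that the stated aim is change over time, and a constant block shift drops out of the time-by-treatment contrast. That stands under an identity link. However, the same sentence also promises between-treatment differences over all time points, and those comparisons do carry the shift.

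It is also fair to say that the documents mention no shift. If there is none, nothing is lost by omission and the block term costs about 2-3% in SD. If time means study session 1 to 15, block is partly or wholly absorbed, but as a factor this brings the sparse cells shown above. Either way, the plan has to say which it means.

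A reader might infer that omitting block biases the treatment effects. The documents do not support that: order is randomised, and the simulated bias with complete data was zero. Treatment-related dropout could add some bias to the level contrasts, but no dropout rate is given. Differential carry-over is a separate problem that a block term would not cure.

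A reader might also infer that a Session 1-adjusted model should be the main analysis. For an assumed 0.4 SD effect, simulated power rises from 36/48/69% to 46/55/71% at r = 0.3/0.5/0.7. But the first set applies a small-sample variance correction to the change score that the plan does not contain. Against the uncorrected test it is 44/56/76%, with 6-7% null rejections, which is a separate defect.

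Adjustment is also not neutral to carry-over, since blocks may be only one week apart. With an assumed 0.5 SD carry-over from active blocks lasting the whole next block, the adjusted contrast is biased by −0.10, −0.08 and −0.05 SD and the change score by about zero. If carry-over touches Session 1 only, the change score is biased by about +0.16 and the adjusted contrast by +0.05, +0.07 and +0.10. Neither approach dominates.

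**Conclusion.** The point holds as a specification gap worth closing. The analysis of a three-block crossover names no block term, the covariate search cannot supply one, and time is undefined. With complete data and randomised order, the loss is precision in comparisons between treatments at a session. Relative to 0.205 with the term, the SD rises by about 5% (0.215/0.205) at a 0.25 SD shift per block and by about 24% (0.255/0.205) at 0.5 SD.

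These sizes rest on assumed variances and shifts and on an identity link; another link could change them and the cancellation in the change contrast. The case for Session 1 adjustment is weaker. Its advantage depends on time being categorical and on r, and it trades one carry-over sensitivity for another. The documents do not make it the better primary model.

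**What to change.** In the STATISTICAL ANALYSIS section:

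- Define time as session within block, and state in advance whether it is categorical or linear.
- Add block (1, 2, 3) as a prespecified fixed factor, outside the AIC selection. With categorical sessions this takes the mean model from 15 to 17 parameters for outcomes measured at five sessions, and from 9 to 11 for the isokinetic test (Sessions 1, 3 and 5).
- As a secondary or sensitivity analysis only, report the treatment-by-session contrast at the sessions after Session 1, adjusted for the block's Session 1 value and the participant's mean Session 1 value. This applies to the FSS and the isokinetic test, and to the NPQ if it is modelled the same way. Show it beside the change contrast and state that the two respond differently to carry-over.

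The cost is SAP wording and two parameters with 20 clusters, or about 2-3% in SD if there is no block shift. No new visit or measurement is needed.

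### Differences within and between conditions are tested at 0.05 for each outcome with no primary outcome, session, contrast or multiplicity rule, so the family-wise error is not held at 5%

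*Combined protocol and SAP*

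**What the plan says.** The STATISTICAL ANALYSIS section plans GEE models clustered on subject, with a time-by-treatment interaction. On what is tested it says: "An interaction term between time and treatment will allow us to test the within and between-treatment differences over all time points". On the level it says: "Statistical significance will be assessed at the $\alpha = 0.05$ level". Models are fitted unadjusted and adjusted, with covariates selected by AIC separately for each outcome and the link chosen from histograms.

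No outcome, session or contrast is placed first. There is no testing order, no gate and no adjustment for multiplicity. The section describes its outcomes only in general terms (fatigue, quality of life) and does not mention pain, although the trial title names pain and fatigue together.

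The design facts are in the study description: "20 participants will need to complete 3 randomly-ordered blocks of protocols (sham, 2 mA, 4 mA), separated by at least one week", and "Each block involves 5 daily sessions at the INPL". FSS, NPQ and the isokinetic fatigue test are done before stimulation in Session 1. In Sessions 2 and 4 participants receive the treatment, "after which they will complete the fatigue and pain questionnaires (FSS and NPQ". Session 3 adds the isokinetic test before stimulation. Session 5 has stimulation, then the isokinetic test, then the questionnaires.

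**The concern.** A rule that covers differences inside each condition, differences between conditions and every time point, repeated for each outcome at an unadjusted 0.05, offers many chances to reject. With 20 completers and nothing ranked first, a significant result at one session on one scale could not be told apart from chance. Nor could a reader of the results know which test the trial was meant to be judged on. What is at stake is whether any claim about 2 mA or 4 mA carries the 5% error rate that the plan appears to promise.

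**Working it through.** There is no family-wise figure in the plan to reproduce, and the sample size of 20 has no stated power, effect size or SD behind it. The check counts the contrasts and then finds the chance of at least one rejection when nothing is going on. Sidedness is not stated; two-sided tests are assumed.

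**1. Count.** Three conditions give 3 within-condition changes from Session 1 and 3 pairwise between-condition differences, so 6 contrasts per post-baseline session.
- FSS, Sessions 2 to 5: 4 × 6 = 24.
- NPQ, Sessions 2 to 5: 4 × 6 = 24.
- Isokinetic fatigue test, Sessions 3 and 5: 2 × 6 = 12.
- Total: 24 + 24 + 12 = 60, of which 30 are within and 30 between.

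That these three are the analysed outcomes is an assumption from the visit schedule. The two fatigue measures alone (FSS and the isokinetic test) give 24 + 12 = 36.

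**2. If the tests were independent**, the family-wise error for m tests is 1 − 0.95^m.
- m = 60: 95.4%, with 60 × 0.05 = 3.0 false positives expected.
- m = 36: 84.2%.
- m = 24: 70.8%.
- m = 3 (one overall interaction test per outcome): 14.3%.
- m = 2 (the same, fatigue measures only): 9.75%.

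**3. Allowing for correlation.** The contrasts share participants and sessions, so crossover data were simulated with no stimulation effect and no time effect: 20 participants, 3 conditions, 5 sessions, 3 outcomes, correctly sized paired t contrasts, 4,000 runs per setting. The variance shares and cross-outcome correlations are assumptions. Entries are the chance of at least one rejection.

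| Subject share | Block share | Outcome corr. | All 60 | 30 between | 30 between, change from Session 1 | FSS only (24) |
|---|---|---|---|---|---|---|
| 0.5 | 0 | 0 | 90.2% | 72.5% | 68.3% | 59.7% |
| 0.5 | 0.2 | 0.3 | 90.1% | 68.3% | 66.5% | 61.8% |
| 0.5 | 0.4 | 0.5 | 85.5% | 51.8% | 63.9% | 56.8% |
| 0.5 | 0.45 | 0.5 | 82.0% | 44.7% | 62.6% | 52.1% |
| 0.5 | 0.45 | 0.8 | 74.8% | 37.3% | 53.7% | 52.8% |
| 0.6 | 0.1 | 0.8 | 82.3% | 60.5% | 56.2% | 61.1% |

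A separate simulation gave 72 to 90% for all 60 contrasts and 43 to 71% for the 30 between-condition contrasts. The rounded ranges of about 70 to 90% and 37 to 73% cover both.

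**4. Small-sample size of the planned tests.** Step 3 uses correctly sized tests. An uncorrected robust Wald test with 20 clusters is not correctly sized. The following assumes normal data and complete blocks.
- One paired contrast: 2 × P(t with 19 df > 1.96 × √(19/20)) = 7.1%.
- One 2-df comparison of three conditions: the critical value 5.991 becomes F = 5.991 × (19/20) × 18/(19 × 2) = 2.70, and P(F(2,18) > 2.70) = (1 + 2 × 2.70/18)^(−9) = 9.5%.

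With the uncorrected robust test in step 3, the chance for all 60 contrasts rises to about 86 to 96%.

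**The case against.** The strongest reply is that the plan speaks of a single interaction term and later of the relationship between that interaction and each outcome. This can be read as one overall test per outcome, with contrasts only descriptive. On that reading the figure is about 14% for three independent outcomes, before any small-sample inflation. The reading is possible, but the plan does not state it, and the quoted sentence refers to differences both within and between treatments. The ambiguity limits the headline figure; it does not restore 5%.

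Three further points stand.
- The outcome set is assumed, since the analysis section does not name NPQ or pain.
- Half of the 60 contrasts are within-condition changes. Placebo response, practice or regression to the mean could make these real without any stimulation effect, so the 70 to 90% figure needs a null of no time effect as well. The between-condition contrasts do not, provided any time effect is common to the conditions.
- For the comparisons that matter most, the rates are lower. In a simulation with subject share 0.4 to 0.6, block share 0.1 to 0.4 and outcome correlation 0 to 0.5, the 20 active-versus-sham contrasts gave at least one rejection in 42 to 60% of trials, and at least one favouring active stimulation in 21 to 36%.

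A reader might therefore infer that a false claim of benefit is more likely than not. The documents do not support this. It depends on the per-contrast reading, on the assumed outcomes and on the stronger null, and the between-condition figures fall on both sides of 50%.

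It could also be said that this is a small exploratory trial. The documents do not call it that, and they set a significance level.

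**Conclusion.** The concern holds in this form: the plan sets a per-test level of 0.05 over an unranked set of tests, and the family-wise error is above 5% on every reading considered. The size depends on the reading:
- About 70 to 90% if all 60 post-baseline contrasts are tested and there is neither a stimulation effect nor a time effect.
- About 37 to 73% for the 30 between-condition contrasts.
- About 14% for one overall test on each of three independent outcomes.

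These rest on the assumed correlations, on three outcomes taken from the visit schedule, and on correctly sized tests. They leave out Session 1 comparisons, the choice between unadjusted and AIC-selected models, and the choice of link.

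It is also tempting to infer that naming a primary test would by itself bring the error to 5%. Under the planned GEE with 20 clusters it would not: an uncorrected robust 2-df test has size about 9.5%.

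**What to change.** Amend the STATISTICAL ANALYSIS section as follows.
1. List the analysed outcomes and name one as primary. The choice between the pain and fatigue measures is the sponsor's; if NPQ is chosen, it must be added to the outcomes the section covers.
2. Name one primary time point: Session 5 as change from that block's own Session 1 value. The schedule already collects both for FSS, NPQ and the isokinetic test.
3. Compare the three conditions on that change with a single 2-df time-by-treatment contrast at 0.05. Use a small-sample correction for 20 clusters, for example a bias-corrected sandwich variance with an F reference. Fix the link and covariates for this test in advance.
4. Only if that test is significant, test 4 mA against sham, 2 mA against sham and 4 mA against 2 mA, each at 0.05 with the same correction. With three conditions, any two pairwise nulls together imply the global null, so this is a closed procedure. It holds the family-wise error at 5% to the extent that the component tests are correctly sized.
5. Report all other outcomes, sessions and within-condition changes as secondary estimates with 95% intervals.

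Bonferroni over all 60 contrasts would also control the error, but at 0.05/60 = 0.00083 per test, which is severe for 20 participants.

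The cost is plan wording and a specified correction in the analysis code; no extra participants, visits or measurements are needed. The downside is that fewer results can be called significant, pairwise claims must pass the 2-df test first, and one outcome must be ranked above the other although the title names both pain and fatigue. The documents give no inputs from which to judge the power of the primary test with 20 completers.
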